Eligibility Criteria: Inclusion criteria: Patients with age of 7 to 17 years-old who require a CT scan with IV contrast. Exclusion criteria: Patients with history of seizures, cardiovascular disease, presenting as a trauma, a history of anaphylaxis to lidocaine, or children/adolescents with underlying neurodevelopmental conditions which would interfere with their ability to respond to pre and post IV contrast pain assessments.

Design: This is a prospective, double-blinded randomized control study that will be comparing intravenous lidocaine to a placebo. Patients will be randomized with block randomization. The randomization list will be generated EM Research Manager and given to the EM pharmacist a priori of commencement of the study. The EM Research Manager and EM Pharmacist are not blinded to the study. Once a potential subject has been identified, a member of the research team will obtain consent from the parent or guardian of the subject. The research team member involved with consent and data collection, provider, and subject will all be blinded to which treatment arm they are assigned.

The research team members will monitor each patient and in conjunction with the pharmacy will deliver the assigned treatment to the subject's nurse to administer 10 min prior to the CT scan. If selected for the treatment group, the patient will receive a 1mg/kg IV dose of lidocaine with a max dose of 40mg.¹⁵ A patient selected to the control group will an equal volume of normal saline infused. A research team member will be present during the administration of assigned treatment until the completion of the CT scan. The

patient will be placed on a cardiopulmonary monitor for the duration of this period. Advanced airway equipment, IV midazolam, and IV intralipids will also be available at bedside during infusion and until completion of CT scan to treat any potential adverse effect associated with lidocaine.

Nominal variables to be collected include gender, chief complaint, pain score at triage, use of pain medication at triage and during the ED course, diagnosis, type of CT scan performed, pre and post-intervention pain score, post-intervention pruritus score, post-intervention burning pain score. The only continuous variable being collected includes age (in years-old).

There will be no interruption or deviation from the standard of clinical care provided to each subject. This study will be run completely in the Pediatric Emergency Department.

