Data Collection Procedures: Once a subject has been enrolled, the research team member will review the chart and collect all pertinent information as shown in the data collection template. A questionnaire will be completed prior to administration of the medication as well as following the CT scan which will be administered by the research team member. We will use a combination of the Baker-Wong FACES pain scale and 1 to 10 numerical scale for pain as well as a 5-point Likert scale for discomfort. Once all data has been collected, it will be recorded in password protected document located on a secure server only accessible to members of the research team. All information about the patients will be de-identified. Study investigators will record pain scores, vital signs, and adverse effects at prior to intervention, immediately following intervention, and 15 min following the intervention

The preparing ED pharmacist, research manager, and statistician will be the only ones with knowledge of the study arm to which each participant would be randomized. Treating providers, participants, and the data collecting research team will be blind to the medication route received.

All data will be recorded on data collection sheets, including patients' gender, demographics, medical history, and vital signs, and entered into SPSS (version 27.0; IBM Corp) by the research manager. Development of the randomization list, confirmation of written consent acquisition for all participants, and statistical analyses will be conducted by the research manager and statistician who will work independently of any data collection.

Patients will be closely monitored for any change in vital signs and for adverse effects during the entire study period (up to 120 minutes) by study investigators.

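### Scores are collected blind, but SPSS entry and analysis are assigned to people who know the arm, with no database lock or coded-arm step described

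*Combined protocol and SAP*

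**What the plan says.** The Design paragraph under Study Design sets out the blinding at the bedside: "The research team member involved with consent and data collection, provider, and subject will all be blinded". It also states who is outside the blind. "The randomization list will be generated EM Research Manager and given to the EM pharmacist", and "The EM Research Manager and EM Pharmacist are not blinded to the study".

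Data Collection Procedures repeats that providers, participants and the collecting team are blind. It then lists those who know each participant's arm, and adds the statistician to the pharmacist and the research manager. The collected data are "entered into SPSS (version 27.0; IBM Corp) by the research manager". List development, confirmation of consent and the statistical analyses are given jointly to the manager and statistician, who are to be kept apart from the collecting of data. The section also provides for a password-protected record on a secure server, open only to the research team, and for de-identification of patients. It does not say who makes the server record.

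The outcomes are subjective. The Design paragraph lists pain scores before and after the intervention, together with "post-intervention pruritus score, post-intervention burning pain score". Data Collection Procedures describes a FACES scale combined with a "1 to 10 numerical scale for pain as well as a 5-point Likert scale for discomfort".

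**The concern.** Blinding protects a subjective outcome only as far along the chain as it extends. Here it covers the moment the child gives a score and stops there. The step that turns the score into a database value belongs to the person who made the list. The step that turns database values into a treatment comparison belongs to that person and a statistician who also knows the arms.

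Two kinds of decision are exposed. An illegible, contradictory or out-of-range value on a collection sheet has to be coded by someone, and that person would know the arm. Any analysis choice that the plan leaves open would also be made with the arm known. Neither requires bad intent, and masking both costs little.

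**Working it through.** No arithmetic applies. The documents give no figure that bears on this point and do not say how many entries might be unclear. The check is to follow the data from bedside to result and ask at each stage who acts, whether that person knows the arm, and what safeguard is described.

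- **Collection.** Done by the research team, blinded according to both the Design paragraph and Data Collection Procedures. No problem.
- **Secure-server record.** Described in Data Collection Procedures with nobody named as making it. It may or may not be made by a blinded person.
- **SPSS entry.** Assigned to the research manager, who is unblinded by the Design paragraph's own statement. The sentence links entry to the data collection sheets and does not mention the server record. No check of entries against the sheets is described.
- **Analysis.** Assigned to the manager and statistician, both named among those who know the arm. Data Analysis mentions neither coded arms nor a lock before allocation is merged.

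Next, the provisions that might close the gap:

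- Keeping the two roles away from data collection keeps them from influencing how a child answers. It does not mask them when the answers are entered or analysed.
- Password protection controls access. De-identification removes the patient's identity. Neither is stated to conceal the arm.
- The mixed model in Data Analysis is offered for participants lost to follow-up. It does not govern how a doubtful recorded value is coded.

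Last, whether there is anything left to decide:

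- **At entry.** Two pain instruments are combined without a stated rule for reconciling them. A zero written on a sheet would lie outside the stated numerical range.
- **At analysis.** No primary outcome or time point is named. Pain scores are listed among nominal variables but analysed with t-tests and a mixed model. Categorical outcomes are compared at 30 minutes, while scores are scheduled before the intervention, "immediately following intervention, and 15 min following the intervention".

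So there is real, if modest, discretion at both steps.

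The two sections also differ on roles. The Design paragraph names the manager as list generator, and names the manager and pharmacist as unblinded. Data Collection Procedures gives list development to the manager and statistician, and places the statistician among those who know the arm.

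**The case against.** The best defence is that the outcomes are scores given to blinded staff by blinded children, most of them on closed scales. Copying a number leaves little room for judgement. The data collection template, which is cited but is not in the text available here, may fix the response codes. A blinded team member may make the secure-server record, so a blinded transcription may already exist. An entry check or lock may sit in an operating procedure outside these documents. The manager and statistician may also divide their joint tasks, so that not both do each one.

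Much of this stands, and it is why the risk is limited. It does not remove the point. SPSS entry by an unblinded person and a statistician who knows the arm are stated assignments, not inferences from silence. A server record made by a blinded person would help only if the analysis file were built from it, and the text does not say so.

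A reader might go further and infer that the trial is not double-blind, or that its results will be biased. The documents do not support either reading: participants, providers and score collectors are blinded, the unblinded roles are openly disclosed, and nothing shows that an entry would be altered.

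A reader might also try to measure the problem by counting the unblinded steps or the outcomes affected. Such counts are not safe. The server record is assigned to nobody. The discomfort scale may be the instrument for burning and pruritus rather than a further measure. The recording times are not consistent across sections.

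It could also be argued that, with a lock and coded arms, the statistician may keep the list. That fails, because coding masks nothing from an analyst who holds the key.

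**Conclusion.** The point holds in limited form. Blinding ends at collection, and the documents assign SPSS entry to an unblinded manager and the analyses to two people who know the arm, with no lock or coded-arm step described. What is at stake is how unclear entries and open analysis choices are resolved for subjective scores. The direction and size of any bias cannot be computed, and there is no evidence that bias would occur.

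This rests on two assumptions: that the sections describe actual practice, and that no outside procedure adds a lock or check. If one does, a sentence citing it would answer that part, but the role assignments would still stand. The change is a cheap improvement, not a condition for the trial to be interpretable.

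**What to change.** Amend Data Collection Procedures as follows.

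1. A blinded research team member, not the manager, enters the scores and resolves unclear entries. The text should also name who makes the secure-server record and say whether the SPSS file is built from it.
2. The database is locked before allocation is merged.
3. The list stays with the manager and pharmacist, as the Design paragraph already has it. After lock the manager supplies allocation coded A and B, and the statistician, who does not hold the list, runs the between-group analysis on the coded arms.
4. The Design paragraph and Data Collection Procedures are made to agree on who makes the list and who knows the arm.

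A second blinded person checking entries against the sheets is optional.

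The cost is some entry time for the blinded team, a lock step, and loss of the manager's help with the between-group analysis. The change uses roles already named, and the Design paragraph speaks of team members in the plural ("The research team members will monitor each patient"). Staffing is not stated, so availability must be confirmed. Coding the arms hides only which arm is which. It does not replace naming a primary outcome and time point, which is a separate matter.

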Data Analysis: Data analyses will include frequency distributions, paired t-test to assess a difference in pain scores within each group, and independent-sample t-test to assess differences in pain scores between the 2 groups at the various intervals. Mixed-model linear regression will be used to compare changes in pain numeric rating scale across time points. This will compensate for participants lost to follow-up and allow all patients' data to be analyzed on an intention-to-treat principle. For categorical outcomes (e.g., complete resolution of pain), a χ^2 or Fisher's exact test will be used to compare outcomes at 30 minutes. Percentage differences and 95% confidence intervals between the treatment groups will be calculated for all time points with $P < 0.05$ to denote statistical significance.

REFERENCES

2. Health C on PA of C and F, Task Force on Pain in Infants C. The Assessment and Management of Acute Pain in Infants, Children, and Adolescents. *Pediatrics*. 2001;108(3):793-797. doi:10.1542/peds.108.3.793
3. Wilson-Smith EM. Procedural Pain Management in Neonates, Infants and Children. *Rev Pain*. 2011;5(3):4-12. doi:10.1177/204946371100500303

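### No primary outcome, time point, deciding analysis or multiplicity rule: with about four between-arm tests at P < 0.05, the chance of a false-positive difference in either direction is about 9–19%, not 5%.

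*Combined protocol and SAP*

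**What the plan says.** The Hypothesis section makes one directional prediction covering both pain and discomfort, with no scale, time or test attached. The Study Objectives are general aims.

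The Data Analysis section lists:

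- within arms, a "paired t-test to assess a difference in pain scores within each group";
- between arms, an "independent-sample t-test to assess differences in pain scores between the 2 groups at the various intervals";
- for repeated scores, a model whose between-arm contrast is left undefined: "Mixed-model linear regression will be used to compare changes in pain numeric rating scale across time points";
- for categorical outcomes, with complete pain relief given only as an example, a chi-square or Fisher test that "will be used to compare outcomes at 30 minutes";
- effect estimates, as differences in percentages with 95% intervals, that "between the treatment groups will be calculated for all time points", P < 0.05 being the significance threshold.

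On measurement, Data Collection Procedures has pain scored before the intervention, "immediately following intervention, and 15 min following the intervention". On instruments it says: "We will use a combination of the Baker-Wong FACES pain scale and 1 to 10 numerical scale for pain", and it adds a 5-point Likert scale for discomfort. The Design paragraph also lists a "post-intervention pruritus score, post-intervention burning pain score". None of these sections ranks the outcomes, times or tests, and none gives a multiplicity rule.

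**The concern.** Suppose one between-arm result falls below 0.05 and the others do not. The plan gives no basis for saying whether the hypothesis has been supported, so the deciding result can be chosen once the data are seen. The error rate attached to the trial's conclusion is then higher than the stated 0.05. The opening is real here, because Data Collection Procedures says that the research manager and statistician know the allocation and also run the analyses.

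Three features make it worse:

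- The categorical test is set at 30 minutes, a time at which no pain score is listed.
- Two pain scales are in use, and only the mixed model names its scale.
- Discomfort, pruritus and burning are collected with no test or rank assigned.

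The within-arm paired tests add a further route to a misleading claim. A significant change in one arm and not in the other does not compare the arms.

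**Working it through.** **The plan's own figure.** The documents give no sample size, power or overall error rate, so there is nothing to reproduce beyond the per-test threshold of 0.05. Sidedness is not stated; two-sided is assumed.

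**Counting the between-arm tests.** Two t-tests after treatment (immediately and at 15 minutes), one mixed-model contrast and one categorical test make four. The baseline comparison and the within-arm paired tests are not counted. The list of categorical outcomes is open-ended, so the actual number could be higher.

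**Independent tests (ceiling).**

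- Either direction: 1 − 0.95^4 = 0.185.
- Favouring lidocaine: 1 − 0.975^4 = 0.096.

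**Correlated tests.** For k equally correlated standard normal statistics with correlation ρ and c = 1.96, the chance of at least one false positive is

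1 − ∫ [Φ((c − √ρ·x)/√(1−ρ)) − Φ((−c − √ρ·x)/√(1−ρ))]^k φ(x) dx.

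For the direction favouring lidocaine, the bracket becomes the single term Φ((c − √ρ·x)/√(1−ρ)). With k = 4:

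| ρ | Either direction | Favouring lidocaine |
|---|---|---|
| 0 | 18.5% | 9.6% |
| 0.5 | 15.6% | 7.8% |
| 0.7 | 13.0% | 6.5% |
| 0.9 | 9.4% | 4.7% |
| One pre-named test | 5.0% | 2.5% |

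**Simulation on the same children's scores.** The correlation between the tests depends on how they share data, so trials with no true effect were simulated at patient level, 20,000 per setting. All inputs are assumptions: 30 or 60 children per arm; a 1–10 score with mean 4 and SD 2.5 before rounding; within-child correlation 0.3 to 0.9. The tests were a t-test at each of two post-drug times, the arm difference in mean change from baseline (standing in for the mixed model with complete data), and chi-square/Fisher on the lowest score at the last time.

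- Either direction: 13.9–15.7% with 30 per arm and 15.3–16.8% with 60 per arm.
- Favouring lidocaine: 7.1–8.6% overall.

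A second simulation, with 30 or 50 per arm and within-child correlation 0 to 0.9, gave about 14–18% in either direction.

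**If the symptom scores were tested too.** Adding discomfort, pruritus and burning makes seven tests: 11.4% (ρ = 0.9) to 1 − 0.95^7 = 30.2% (independent). The Data Analysis section does not state that these will be tested, so this only shows what the lack of ranking leaves open.

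**The case against.** **The mixed model could be read as the intended main analysis.** It is the only method tied to handling loss to follow-up and intention-to-treat, and the only one that names its scale. But it is never called primary, its arm or arm-by-time contrast is undefined, and P < 0.05 is not reserved for it. This softens the point without answering it.

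**The count of four can be challenged, and this has force.** The 30-minute test has no matching pain score. The Design paragraph also has study drug given 10 minutes before the scan. If the intervention means study drug, the immediate score precedes contrast and does not test the hypothesis. Dropping tests gives:

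- Three tests, by formula: 8.4% (ρ = 0.9) to 1 − 0.95^3 = 14.3%.
- Without the categorical test, simulated: 12–14%.
- Without the immediate test, simulated: 11–13%.
- Without both, simulated: 9–10%. As a check, with equal variances a score at one time and its change from baseline correlate at √((1−r)/2), where r is the within-child correlation. That is 0.59 for r = 0.3 and 0.22 for r = 0.9. The two-test formula gives 8.75% at ρ = 0.6 and 9.5% at ρ = 0.3, in line with the simulation.

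The size depends on the count; the inflation remains in every version.

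**The ends of the range are extreme.** The 19% end needs independent tests, which these are not, and the 9% end needs test statistics correlated at 0.9. The simulated 14–17% is the better guide for four tests.

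**Direction.** For a directional hypothesis, the risk of a false claim of benefit is the more relevant figure. It is 5–10% against 2.5%, and the either-direction range should not be read as that risk.

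**Conclusion.** The concern holds and should be corrected before any comparison by arm. No section names a primary outcome, scale, time point, deciding analysis or multiplicity rule, and the times for pain scores and for the categorical test disagree. This is more than missing detail: applying the stated P < 0.05 rule to every planned test inflates the error rate.

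For four two-sided tests the chance of at least one false-positive difference is 9–19%, most plausibly 14–17%, against 5%. A false claim of benefit has a chance of 5–10%, most plausibly 7–9%, against 2.5%. These figures assume no true effect, the count of four, two-sided testing and the correlations shown. With only two or three usable tests the either-direction rate is still about 8–14%. The lack of a deciding analysis does not depend on any of these assumptions.

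**What to change.** Before any comparison by arm, amend the protocol/SAP as follows.

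1. Name one primary between-arm analysis. An example is the numeric pain score at one stated post-contrast assessment, from a single baseline-adjusted model at two-sided 0.05. The sponsor should confirm the scale and the time. This holds the error rate at 5% (2.5% favouring lidocaine).
2. Reconcile the 15-minute time in Data Collection Procedures with the 30-minute time in Data Analysis, and say whether times run from study drug or from contrast.
3. Make all other scales, symptoms, times and tests secondary. Either adjust them by Holm's method, or report estimates with 95% confidence intervals and make no significance claims.
4. State that the within-arm paired t-tests are descriptive and are not evidence of efficacy.

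The cost is wording, with no extra patients or visits. The downside is that secondary outcomes can no longer be called significant at an unadjusted 0.05. If the sponsor keeps 30 minutes, a pain score at that time must be added to data collection, and it cannot be recovered for children already studied.

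### Between-arm pain t-tests ignore the pre-intervention pain score, and the mixed model's arm and baseline terms are not stated; adjusting costs about one degree of freedom and may gain precision

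*Combined protocol and SAP*

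**What the plan says.** The Data Analysis section gives two between-arm analyses of pain. The first is an "independent-sample t-test to assess differences in pain scores between the 2 groups at the various intervals". No covariate is named. The second is a longitudinal model: "Mixed-model linear regression will be used to compare changes in pain numeric rating scale across time points". That sentence does not say whether the model contains an arm term or an arm-by-time term, or whether the pre-intervention score enters as a response or as a covariate. Neither analysis is named as primary, and no adjusted analysis appears elsewhere.

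A baseline is available. The Design section lists the "pre and post-intervention pain score" among the variables. Data Collection Procedures states that "A questionnaire will be completed prior to administration of the medication as well as following the CT scan", and separately that investigators will "record pain scores, vital signs, and adverse effects at prior to intervention, immediately following intervention, and 15 min following the intervention". On the instrument it says: "We will use a combination of the Baker-Wong FACES pain scale and 1 to 10 numerical scale for pain".

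**The concern.** The Hypothesis section asks whether lidocaine, compared with saline, lowers pain and discomfort after contrast. That is a single comparison of arms, and the plan leaves open how it will be made.

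- The t-test compares raw post-intervention scores and ignores where each patient started.
- If the mixed model treats baseline as a repeated outcome with its own free arm effect and categorical time, its arm-by-time contrast is a comparison of change scores.
- If baseline is a covariate, or the two arms are constrained to a common baseline mean, the model has about the precision of ANCOVA.

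These can differ substantially in precision, and the choice could be made after the data are seen. Taken literally, testing at all intervals would also allow a test of the arms against each other before treatment, which says nothing about the drug.

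**Working it through.** **Inputs.** The documents give no sample size, SD, target effect or pre-post correlation, so there is no planned figure to reproduce. The significance level is 0.05 (Data Analysis). I assume a two-sided test, 1:1 allocation, and rho of 0, 0.2, 0.3, 0.5 and 0.7. Write L for the ratio of pre-intervention SD to post-intervention SD, and N for the total sample size.

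**Variance of the between-arm difference, relative to the raw t-test**

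- ANCOVA: 1 − rho², whatever L is. For example, rho 0.5 gives 1 − 0.25 = 0.75.
- Change score: 1 + L² − 2·rho·L. With L = 1 this is 2(1 − rho); rho 0.3 gives 1.4.
- Difference between the two: (1 + L² − 2·rho·L) − (1 − rho²) = (L − rho)², which is never negative. In large samples ANCOVA is therefore never less precise than the change score or the raw score.

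**Power.** Suppose the raw t-test has 80% power, so the noncentrality is 1.96 + 0.84 = 2.80. By the normal approximation, the power of another analysis is Φ(2.80/√ratio − 1.96).

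| rho | ANCOVA variance | ANCOVA CI width | ANCOVA power | Change-score variance, L = 1 | Change-score power, L = 1 |
|---|---|---|---|---|---|
| 0 | 1.00 | 1.00 | 80% | 2.0 | 51% |
| 0.2 | 0.96 | 0.98 | 82% | 1.6 | 60% |
| 0.3 | 0.91 | 0.95 | 84% | 1.4 | 66% |
| 0.5 | 0.75 | 0.87 | 90% | 1.0 | 80% |
| 0.7 | 0.51 | 0.71 | 97% | 0.6 | 95% |

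The change score depends on L. Over the same rho values its variance ratio is 1.25, 1.05, 0.95, 0.75 and 0.55 at L = 0.5, and 5.0, 4.2, 3.8, 3.0 and 2.2 at L = 2. The documents do not say which L applies; these values only show the sensitivity. With equal SDs, the change score beats the raw t-test only when rho exceeds 0.5.

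**Cost of adjusting in a finite sample.** One linear covariate takes the residual degrees of freedom from N − 2 to N − 3. The expected variance is multiplied by (N − 3)/(N − 4) = 1 + 1/(N − 4). Setting (1 − rho²)(N − 3)/(N − 4) = 1 gives a break-even rho of √(1/(N − 3)).

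| Assumed N (total) | Worst-case loss, rho = 0 | Break-even rho |
|---|---|---|
| 20 | 1/16 = 6.2% | 0.24 |
| 50 | 1/46 = 2.2% | 0.15 |
| 100 | 1/96 = 1.0% | 0.10 |

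**Simulation check.** With 20,000 trials at N = 60, rho 0.5 and equal SDs, the variances were 0.0673 (raw), 0.0671 (change) and 0.0514 (ANCOVA). The ratio 0.0514/0.0673 = 0.76 agrees with 0.75 × 57/56 = 0.763. In null simulations at 25 and 50 per arm, type I error was 4.7–5.2% for the raw t-test and 4.8–5.2% for ANCOVA.

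**Where rho might lie.** Reasons for a low value: the covariate is pain before the drug, the target is discomfort caused by contrast, and the plan records "use of pain medication at triage and during the ED course", so pain relief may intervene. Reason for a higher value: Background and Significance says these scans are mostly done for suspected appendicitis, so pain from the illness may persist into the post-CT rating. The documents do not settle this.

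**The case against.** The strongest reply is that no error has been shown. The t-test is valid, its type I error is right, and the plan also has a longitudinal model that probably uses the pre-intervention score in some form. On that view, what remains is an under-described model and an efficiency preference whose benefit in this trial cannot be demonstrated. The trial-specific reasons for a low correlation are real, and at rho up to 0.2 the gain is at most 4% of variance. The reduction to a change-score contrast also needs a particular model form that the plan does not state.

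Much of this stands. The point concerns precision and pre-specification, the benefit may be negligible, and the change-score figures show what the wording permits, not what the sponsor intends. Three further limits also stand:

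- In a very small trial (N = 20) the worst-case loss is about 6%, so the claim that adjustment is nearly free fits moderate sizes better.
- The pruritus and burning scores are listed as post-intervention only, so they have no matching baseline and this remedy does not reach them.
- The lack of a named primary analysis is a wider gap, of which this is one part.

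None of this favours the unadjusted test. The possible loss is small, the possible gain is not, and the covariate is already collected.

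**Conclusion.** The concern holds, as a change that should be made and not as a flaw that invalidates the trial. The one explicit between-arm test of pain leaves out an available baseline, and the mixed model is not specified well enough to show whether it makes good the omission. At moderate sample sizes, ANCOVA is the only one of the three candidate analyses that is never materially worse than the other two. Relative to the raw t-test it saves 0–4% of variance for rho 0 to 0.2, 9% at 0.3, 25% at 0.5 and 49% at 0.7, before a small-sample penalty of 1–2% at 50 to 100 patients in total. These sizes rest on assumed correlations and sample sizes. The facts about the text and the formulas do not.

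**What to change.** In the Data Analysis section, replace the between-arm t-tests on pain with an ANCOVA of the post-CT pain score on arm and pre-intervention pain score. Take both scores from the questionnaire given before the medication and after the CT, and on the same numeric scale. If the mixed model is to carry the comparison, either of these forms is equivalent in purpose:

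- model the post-intervention scores with arm, time, arm-by-time, pre-intervention score and its interaction with time; or
- keep the pre-intervention score as an outcome, with the two arms constrained to a common baseline mean, and include arm-by-time terms.

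State that the treatment effect is read at a time after contrast. The Design section has the "nurse to administer 10 min prior to the CT scan"; if intervention means the study drug, the score taken immediately afterwards may come before contrast. Do not test the arms against each other at the pre-intervention time, and treat the within-arm paired t-tests as descriptive.

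Two items should be reconciled in the same edit. The Design section classes pain scores as nominal and age as the only continuous variable, which does not fit t-tests or linear regression. Separately, Data Collection Procedures stops at 15 minutes while Data Analysis refers to 30 minutes.

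The core change is two or three sentences and one residual degree of freedom. It needs no new data and no change to patient care.
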